3.7.3.6 Monitoring of Noninfectious Pneumonitis [MIRV Cohort]

Noninfectious pneumonitis has been observed after the administration of MIRV. Noninfectious pneumonitis may result in fatigue, shortness of breath, cough, or respiratory distress.

Drug-induced pneumonitis may be immediately life threatening. If a subject presents with signs or symptoms consistent with pneumonitis and/or other clinically meaningful signs or symptoms of pulmonary toxicity, the subject should be immediately evaluated. Subjects are advised to notify their treating physician immediately if they experience new or worsening shortness of breath, cough, or respiratory distress. Subjects who are asymptomatic may continue dosing of MIRV with close monitoring.

The management and treatment guidelines outlined in [Table 10](#) should be followed.

Table 10 Management of Noninfectious Pneumonitis

CTCAE v5.0 Grade	CTCAE v5.0 Definition	Medical Management of Pneumonitis	Guidelines for Dose Modifications ^a
Grade 1	Asymptomatic; clinical or diagnostic observations only; intervention not indicated	
 Radiologic assessments (CT scan and/or chest x-ray) should be performed as clinically indicated. Monitor for pulmonary symptoms. 	
 Continue dosing in asymptomatic subjects and monitor closely.
Grade 2	Symptomatic; medical intervention indicated; limiting instrumental ADL	
 Radiologic assessments (CT scan and/or chest x-ray) should be performed as clinically indicated. Subject must be evaluated by a pulmonary specialist. Treatment with corticosteroids may be indicated as recommended by a pulmonary specialist and/or institutional guidelines. 	
 Hold dosing until symptoms resolve to Grade \leq 1. MIRV may be resumed at same dose level or one dose level lower after discussion with the Sponsor.
Grade 3	Severe symptoms; limiting self-care		
 Permanently discontinue MIRV.

CTCAE v5.0 Grade	CTCAE v5.0 Definition	Medical Management of Pneumonitis	Guidelines for Dose Modifications ^a
	ADL; oxygen indicated	
 • Radiologic assessments (CT scan and/or chest x-ray) should be performed as clinically indicated. • Subject must be evaluated by a pulmonary specialist. • Treatment with corticosteroids until resolution of symptoms may be indicated as recommended by a pulmonary specialist and/or institutional guidelines. • Bronchoscopy with lavage and/or biopsy when clinically feasible should be performed. • The pneumonitis event must be followed until resolution. 	
Grade 4	Life-threatening respiratory compromise; urgent intervention indicated (e.g., tracheotomy or intubation)		

Abbreviations: ADL = activities of daily living; AE = adverse event; CT = computed tomography; MIRV = mirvetuximab soravtansine.

a. Failure to meet retreatment criteria within 1 cycle (21 days) after the missed dose due to insufficient recovery from a treatment-related toxicity will result in treatment discontinuation unless otherwise specified in the management guidance for a particular toxicity

3.7.3.7 Management of Electrolyte Imbalance [MIRV Cohort]

Prompt attention should be given to the correction of potential electrolytes imbalance, especially hypokalemia and hypomagnesemia.

3.7.3.8 Potential Infusion-Related Reactions [MIRV Cohort]

Some subjects treated with IV infusions of therapeutic drugs have experienced concurrent IRR (see CTCAE version 5.0). The signs and symptoms may vary and include, for example, headache, fever, facial flushing, pruritus, myalgia, nausea, chest tightness, dyspnea, vomiting, erythema, abdominal discomfort, diaphoresis, shivers, lightheadedness, hypotension, palpitations, and somnolence. Anaphylaxis might occur at any time during an infusion. Before any infusion is started, appropriate medical personnel, medication (e.g., epinephrine, inhaled beta agonists, antihistamines, and corticosteroids), and other required resources to treat anaphylaxis must be readily available. In general, investigators should manage acute allergic or HSRs according to Institutional practices. General guidelines for the management of acute IRRs and for subsequent retreatment are provided in [Table 11](#). Delayed IRRs may occur; therefore, subjects should be advised to seek immediate medical treatment if symptoms newly develop and/or recur after discharge from clinic.

Table 11 Management Guidelines for Potential Infusion-Related Reaction [MIRV Cohort]

Infusion Reaction CTCAE v5.0 Severity Grade	Management
Grade 1: Mild, transient reaction	
 Maintain infusion rate unless progression of symptoms to Grade ≥ 2; if symptoms worsen, refer to guidelines below. Promethazine (or equivalent) 150 mg PO per day (Q4h) PRN for nausea Diphenhydramine (or equivalent) 25 to 50 mg PO or IV PRN Methylprednisolone (or equivalent) 125 mg IV PRN
Grade 2: Moderate	
 Interrupt infusion and disconnect infusion tubing from subject Promethazine (or equivalent) 150 mg PO per day (Q4h) PRN for nausea Diphenhydramine (or equivalent) 25 to 50 mg PO or IV PRN Acetaminophen (or equivalent) 650 mg PO PRN Methylprednisolone (or equivalent) 125 mg IV PRN After recovery from symptoms, resume the infusion at 50% of the previous rate and if no further symptoms appear, gradually increase rate until infusion is completed. For subsequent dosing in future cycles, subjects should be premedicated with dexamethasone (or equivalent) 8 mg PO BID the day before drug administration and acetaminophen (or equivalent) 650 mg PO, diphenhydramine (or equivalent) 25 to 50 mg PO, and dexamethasone 10 mg IV 30 to 60 min before dosing.
Grade 3: Severe, prolonged reaction not rapidly responsive to symptomatic medication and/or brief interruption of infusion; recurrence of symptoms after initial improvement; hospitalization indicated for clinical sequelae OR Grade 4: Life-threatening consequences, urgent intervention indicated	
 Immediately stop infusion and disconnect infusion tubing from subject. Administer diphenhydramine (25 to 50 mg) IV (or equivalent) Administer IV steroids (methylprednisolone (or equivalent) up to 0.5 mg/kg Q 6h) to treat ongoing reaction and prevent recurrence Administer bronchodilators (nebulized albuterol/salbutamol, 2.5 to 5 mg in 3 mL of saline or equivalent) as medically indicated Administer normal saline as medically indicated Administer epinephrine (0.2 to 0.5 mL of a 1:1000 dilution (0.2 to 0.5 mg) SQ or IM) as medically indicated. Epinephrine should only be used if all other treatment methods fail to manage the IRR. Advise subject to seek emergency treatment and notify investigator/clinic if the infusion-related symptoms recur after discharge from clinic. Report as an SAE (see Section 7.4). Permanently discontinue study medication treatment

Abbreviations: BID = twice a day; CTCAE = common terminology criteria for adverse events; IM = intramuscular; IRR = infusion-related reaction; IV = intravenously; PO = orally; PRN = as needed; SAE = serious adverse event; SQ = subcutaneous

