3.2.2 SL-172154 Administered with Mirvetuximab Soravtansine (MIRV)

SL-172154 (3.0 mg/kg starting dose) will be administered by IV infusion on Day 8 and Day 15 of 21-day cycles. Premedication as prophylaxis for IRR with dexamethasone (8 mg IV), an antipyretic and antihistamines should be administered at least 30 minutes prior to each SL-172154 administration as described in Section 5.1.1. MIRV (6.0 mg/kg AIBW, IV) will be administered on Day 1 of each 21-day cycle. Premedication with antipyretic, antihistamine, and dexamethasone will be administered at least 30 minutes prior to each MIRV administration as described in Section 5.3.2.1. Prophylactic use of eye drops with MIRV administration is described in Section 5.3.2.2.

The planned dose escalation of SL-172154 is outlined in [Table 2](#); additional doses and/or schedules or intermediate doses may be explored based on emerging safety, PK, and PD data. SL-172154 doses explored in SL03-OHD-105 will not exceed the highest dose determined to be safe and tolerable in the monotherapy dose escalation study SL03-OHD-101.

Subjects will be enrolled in cohorts of approximately 3 subjects into sequential dose levels of SL-172154 administered with MIRV and evaluated for DLT during the 21-day DLT evaluation period. DLT criteria are defined in Section 3.5. Treatment will be administered in 21-day cycles until at least one of the study treatment discontinuation criteria is met (Section 3.1.1). During therapy, management of MIRV-related toxicity should follow the guidelines provided in Section 3.7.3 and the MIRV IB or the current USPI, as applicable. Subjects will be followed according to the SOA in Section 6.2.

The safety as well as available PK, PD, and efficacy data from these subjects will inform the dose of SL-172154 selected to be further evaluated in dose expansion when administered in combination with MIRV to subjects with platinum-resistant ovarian, primary peritoneal, or fallopian tube cancer.

Table 2 SL-172154 Dose Escalation Plan When Administered with MIRV

Dose Level ^a	SL-172154 Dose ^b [D8 and D15 in each 21d cycle]	SL-172154 Infusion ^c	Mirvetuximab soravtansine (MIRV) ^e
-1 ^d	1.0 mg/kg	60 min ± 10 min	6.0 mg/kg AIBW, IV administered on Day 1 of each 21-day cycle

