3.7 Toxicity Management Guidelines

All AEs should be assessed using NCI-CTCAE v5.0 criteria. CRS will be graded per the ASTCT Consensus Grading Criteria for CRS (described in Section 3.7.1.2). Ocular AEs for MIRV will be graded per the tables in Appendix Section 16.6. These guidelines are not meant to be prescriptive, and investigators should always use clinical judgement. Investigators should always err on the side of caution if treatment-related toxicity is suspected. Subjects should be thoroughly evaluated to rule out any alternative etiology (e.g., disease progression, concomitant medications, and infections). In the absence of a clear alternative etiology, the possibility of an immune-related AE should be considered.

Every effort should be made to administer study treatment on the planned dose and schedule. If PLD or MIRV dosing is delayed, SL-172154 should also be delayed so that the dosing interval between PLD or MIRV and SL-172154 can be preserved. This will result in the cycle being delayed. If an SL-172154 dose is not given, the dose should be considered skipped, and the cycle should not be delayed. Please consult with the Medical Monitor if further guidance is needed.

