Grade 3	
• Immediately discontinue infusion of SL-172154• Vital signs should be measured after the onset of an IRR approximately every 15 minutes for one hour after discontinuation of SL-172154 infusion and then approximately every 30 minutes for hours 2 and 3 after the discontinuation of the SL-172154 infusion.• Begin IV infusion of normal saline and treat symptoms as indicated and per institutional guidelines e.g., epinephrine, bronchodilators, diphenhydramine, famotidine or other available H2 receptor antagonist, corticosteroids, consider opioids (e.g., meperidine) for rigors, oxygen, fluids, vasopressors, etc. Epinephrine is the drug of choice in an anaphylactic reaction and its administration should not be delayed.• Monitor subjects with close observation in an outpatient or inpatient setting for 12 hours or until recovery from symptoms. Strongly consider admission to hospital.• Rechallenge should not be attempted in cases of true anaphylaxis. In other cases, once the subject has completely recovered, carefully consider if it is safe for the subject to receive SL-172154 at the next scheduled dose with premedication and dose reduction.
◦ Reduce the SL-172154 dose for the next two infusions to 1 mg/kg at $\leq 50\%$ of the rate stated in the protocol. These two subsequent infusions of SL-172154 (after an event of Grade 3 event of IRR) must be administered in an inpatient or outpatient setting with prolonged observation for a minimum of 12 hours after the completion of the infusion.◦ If symptoms do not recur at 1 mg/kg SL-172154 dose, subsequent infusions may be administered at the original rate stated in the protocol. If no further symptoms, the SL-172154 dose may be re-escalated to 3 mg/kg but administered at $\leq 50\%$ of the rate stated in the protocol.
Recurrent Grade 3	
• If the Grade 3 IRR recurred, permanently discontinue SL-172154

General Guidance for Infusion-Related Reactions (IRRs) [Rosello, 2017a]

Grade 4

- Permanently discontinue SL-172154.
- Admit to hospital for close observation until resolution of symptoms.
- Vital signs should be measured after the onset of an IRR approximately every 15 minutes for one hour after discontinuation of SL-172154 infusion and then approximately every 30 minutes for hours 2 and 3 after the completion of the SL-172154 infusion.

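### For anaphylaxis during a MIRV infusion, Table 11 makes epinephrine a last resort, whereas the SL-172154 tables say it should not be delayed; Table 11 needs an anaphylaxis exception

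*Protocol*

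**What the plan says.** Section 3.7.3.8 of the Protocol covers infusion reactions to MIRV. It warns that "Anaphylaxis might occur at any time during an infusion" and requires staff, drugs (epinephrine is the first example given) and other resources to be ready before any infusion starts. It continues: "In general, investigators should manage acute allergic or HSRs according to Institutional practices". The next sentence sends the reader to Table 11 for acute infusion reactions and later retreatment.

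Table 11 has one row for Grade 3 and Grade 4 together. Its upper end is "Grade 4: Life-threatening consequences, urgent intervention indicated". The row lists diphenhydramine, IV steroids, bronchodilators and saline, then epinephrine where medically indicated, and then adds: "Epinephrine should only be used if all other treatment methods fail to manage the IRR". The table does not mention anaphylaxis.

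For SL-172154, the Grade 3 and Grade 4 rows of the infusion-reaction table (Section 3.7.1.1) say: "Epinephrine is the drug of choice in an anaphylactic reaction and its administration should not be delayed". The Grade 3 and Grade 4 rows of the cytokine release syndrome table (Section 3.7.1.2) carry the same sentence. The SL-172154 Grade 3 infusion-reaction row also states: "Rechallenge should not be attempted in cases of true anaphylaxis".

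Section 3.7, which introduces all the toxicity guidance, says: "These guidelines are not meant to be prescriptive, and investigators should always use clinical judgement".

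**The concern.** Within one protocol, the same emergency gets opposite instructions depending on which drug is being infused. If the reaction follows SL-172154, epinephrine comes first and must not wait. If it follows MIRV, the row for the most severe reactions puts epinephrine behind every other treatment.

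This is a subject-safety matter. A site that follows the Table 11 row literally would work through antihistamine, steroid, bronchodilator and fluids before giving epinephrine in an anaphylactic reaction to MIRV. That is the delay the protocol rules out elsewhere.

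**Working it through.** The documents give no figure to reproduce. The check is a comparison of texts, followed by a rough count of exposure.

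**1. Does Table 11 reach anaphylaxis?** Yes, on the natural reading.
- Its parent section names anaphylaxis as an event that can happen during an infusion.
- The signs listed there for an infusion reaction include chest tightness, dyspnea, hypotension, flushing and pruritus. Nothing separates anaphylaxis from other reactions.
- The row expressly includes life-threatening Grade 4 reactions.
- The protocol's other infusion-reaction table treats true anaphylaxis as a case inside its Grade 3 row, so a reader can expect Table 11 to cover it too.

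**2. Does the SL-172154 wording fill the gap?** No. Section 3.7.1 is for events related to SL-172154 and Section 3.7.3 is for events related to MIRV. The drugs are also given on different days: "MIRV (6.0 mg/kg AIBW, IV) will be administered on Day 1 of each 21-day cycle", with SL-172154 on Days 8 and 15. For a Day 1 reaction, Table 11 is the protocol text that applies.

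**3. Where exactly do the texts conflict?**

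| Situation | SL-172154 rows | MIRV Table 11, Grade 3/4 |
|---|---|---|
| Anaphylaxis | Epinephrine is drug of choice, no delay | Epinephrine only after all else fails |
| Other severe infusion reaction | Epinephrine among options, no order set | Epinephrine only after all else fails |

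Only the first line is a contradiction. In the second, the SL-172154 rows set no order of use, so nothing is contradicted.

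**4. How many subjects are exposed?** Sections 3.1.1 and 9.1.4 plan about 12 MIRV subjects in escalation and 64 in expansion: 12 + 64 = 76. Sections 3.3.2 and 9.1.4 allow about 10 more: 76 + 10 = 86. MIRV is 1 of 3 scheduled infusions per 21-day cycle (Day 1, against Days 8 and 15).

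**5. How likely is at least one event?** The documents give no MIRV anaphylaxis rate, so the per-subject rate p is an assumption. With P = 1 − (1 − p)^n:

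| Assumed p | n = 76 | n = 86 |
|---|---|---|
| 0.1% | 7.3% | 8.2% |
| 0.5% | 31.7% | 35.0% |
| 1% | 53.4% | 57.9% |

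These are chances that the situation arises at all. They are not chances that epinephrine is delayed.

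**The case against.** The strongest reply is that Table 11 never names anaphylaxis and its sentence refers only to the infusion reaction. Section 3.7.3.8 can be read as giving three routes: anaphylaxis (have resources ready), acute allergic or hypersensitivity reactions (institutional practice) and acute infusion reactions (Table 11). On that reading the last-resort sentence never applies to anaphylaxis, and the two sets of tables can be followed together. Where the protocol means to cover anaphylaxis in a table, as for SL-172154, it says so.

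Other points also reduce the practical risk:
- The row gives epinephrine as medically indicated.
- Section 3.7 leaves room for clinical judgement.
- Section 3.2.2 also points to the MIRV IB or USPI for MIRV toxicity; neither was available here.
- Premedication before MIRV is mandatory (Section 5.3.2.1), and Section 1.7.1 describes the centers as experienced.
- The probabilities above rest on an assumed rate and do not measure harm from this sentence.

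The last point is correct, and the figures should be read that way. The mitigating texts do make a literal application less likely. The three-route reading is possible, but it does not cancel the instruction. The institutional-practice sentence is qualified as general and leads straight into the reference to Table 11, and the row expressly covers life-threatening reactions. The medically-indicated wording is followed at once by the sentence that restricts it, so the row is in tension with itself. A general appeal to judgement does not correct a specific restrictive rule in an emergency table.

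**Conclusion.** The concern holds. For anaphylaxis during a MIRV infusion, the Table 11 Grade 3/4 row is wrong as written and contradicts the protocol's own SL-172154 guidance. The scope is narrow: anaphylaxis only, and MIRV infusions only.

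The contradiction is established from the text and needs no rate. The likelihood of meeting it in this trial does depend on the assumed 0.1% to 1% per-subject rate. It is a change the sponsor should make on safety grounds. Confidence is high on the conflict in the text; the clinical content still needs confirming against the MIRV IB and USPI.

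**What to change.** In the Grade 3/4 row of Table 11, limit the last-resort sentence to non-anaphylactic infusion reactions, and add the anaphylaxis sentence from Section 3.7.1.1 unchanged. The sponsor's clinicians should confirm the wording and check it against the MIRV IB and USPI.

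The cost is a one-line edit to one table row, with no effect on design, endpoints, sample size or analysis. It could go out first as a protocol memo and enter the next amendment, as the sponsor did for the SL-172154 infusion-reaction guidance (memo of 21-Jun-2024, described in Section 16.10).

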3.8 Subject Withdrawal of Consent

- A subject may withdraw from the study at any time at her own request; or may be withdrawn at any time at the discretion of the investigator for safety, behavioral, compliance, or administrative reasons. The latter is expected to be uncommon. The subject may withdraw consent from further treatment on the study and continue in the survival follow-up (SFU) portion of the study or may withdraw consent from further

participation in the study (e.g., permanently discontinue study treatment, any follow-up study procedures, no longer be contacted for survival).

- At the time of study medication discontinuation, a PTV should be conducted, as shown in the SOA in Section 6.1 and Section 6.2. See SOA for data to be collected at the time of study discontinuation of study treatment and for any further evaluations that need to be completed. Every effort must be made to continue follow-up of subjects for protocol-specified safety follow-up procedures to capture AEs, SAEs, and unanticipated problems.
- If the subject withdraws consent for disclosure of future information, the Sponsor may retain and continue to use any data or biological samples collected before such a withdrawal of consent.
- If a subject withdraws from the study, she may request destruction of any samples taken and not tested, and the investigator must document this in the site study records.

3.9 Lost to Follow-Up

- A subject will be considered lost to follow-up if he or she repeatedly fails to return for scheduled visits and is unable to be contacted by the study site.
- The following actions must be taken if a subject fails to return to the clinic for a required study visit:
 - The site must attempt to contact the subject and reschedule the missed visit as soon as possible and counsel the subject on the importance of maintaining the assigned visit schedule and ascertain whether the subject wishes to and/or should continue in the study.
 - Before a subject is deemed lost to follow-up, the investigator or designee must make every effort to regain contact with the subject (where possible, 3 telephone calls and, if necessary, a certified letter sent to the subject's last known mailing address or local equivalent methods). These contact attempts should be documented in the subject's medical record.
 - Should the subject continue to be unreachable, she will be considered as lost to follow-up and withdrawn from the study.

3.10 Premature Termination or Suspension of Study

The Sponsor reserves the right to close the study site or terminate the study at any time for any reason. Written notification, documenting the reason for study suspension or termination, will be provided by the Sponsor to investigators and the country regulatory authorities as required. If the study is prematurely terminated or suspended, the investigator will promptly inform the Institutional Review Board/Independent Ethics Committee (IRB/IEC) and will provide the reason(s) for the termination or suspension. Study sites will be closed upon study completion. A study site is considered closed when all required documents and study supplies have been collected or destroyed and a study-site closure visit has been performed.

The investigator may initiate study-site closure at any time, provided there is reasonable cause and sufficient notice is given in advance of the intended termination.

Reasons for the early closure of a study site by the Sponsor or investigator may include but are not limited to:

- Failure of the investigator to comply with the protocol, the requirements of the IRB/IEC or local health authorities, the Sponsor's procedures, or Good Clinical Practice (GCP) guidelines
- Inadequate recruitment of subjects by the investigator
- Discontinuation of further development of SL-172154
- Determination of unexpected, significant, or unacceptable risk to subjects

